3.0.4 RANDOMIZATION PROCESS

Caregivers and youth willing to participate will be consented and either complete study entry assessments and randomization or will be consented and then scheduled for an appointment for completion of study entry assessments and randomization at a more convenient time. Caregivers and youth will be randomized to either the caregiver contingency management or treatment as usual group. The proposed urn randomization procedure is a randomization method that aims to achieve balance across groups on factors that, if unaddressed, could bias estimates of the intervention effect. There is an exception to the randomization procedure. Some families will be placed into the caregiver contingency management group for the purpose of training therapists prior to receiving randomized participants.

4.0 RESEARCH DESIGN & METHODS Design Overview:

A well-specified intervention, Contingency Management, will be adapted to reinforce caregiver participation in drug court (CCM). We propose a randomized clinical trial examining the utility of caregiver contingency management to increase caregiver engagement in juvenile drug court and adolescent drug treatment activities. The proposed study follows a 2 (treatment type: Drug Court plus treatment as usual (TAU); Drug Court and TAU plus Caregiver CM [CCM] x 10 (time: pretreatment [T0], 1-month [T1], 2-month [T2], 3-months [T3], 4-month [T4], 5-month [T5], 6-months [T6], 9-months [T7], 12-months [T8], and 18-months [T9-six months post-juvenile drug court involvement]) factorial design, with random assignment of 180 caregivers/youths to one of the two treatment conditions. Repeated measures of caregiver and youth functioning will be collected at pre-treatment (T0), and each of the post-randomization time points (T1 – T9). We choose a randomized trial because this is the most valid way to test the efficacy of our proposed intervention. We choose the follow-up time line to measure short-term and long-term maintenance of change. Our randomization procedure will help mitigate bias across the treatment groups, providing groups that are equally distributed across a number of characteristics known to influence outcomes.

Study Timeline:

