Model building & estimation. The data will be analyzed using MRMs. This approach provides a variety of options for modeling change over time, including linear, non-linear, and phase-specific (e.g., during-treatment, post-treatment) patterns of change. Prior to analysis, each outcome will be graphically and descriptively evaluated to determine the best distribution for modeling. The model building approach detailed by Singer and Willett will be used to specify fixed and random effects. First, a fully unconditional model will be estimated to determine the proportion of within- and between-subject outcome variance. Second, at the repeated measurements level, and informed by the spaghetti plots, growth terms (e.g., linear, quadratic) will be specified to explain the within-subject variance. These terms will be computed using participants' actual assessment dates, tailoring the model to the observed spacing of measurements. 100 Third, the effect of CCM will be modeled by an uncentered, dichotomous indicator (i.e., CCM = 1, TAU = 0) at youth/caregiver level (i.e., level-2), and cross-level interaction effects will be specified between the CCM indicator and the level-1 growth term(s). Before estimating the final model, fixed effect indicators will be included to test for systematic differences across therapists, providers, and districts/judges, and if identified, differences will be statistically controlled in the final model. The analyses will use an intention-to-treat approach, with youth/caregivers retained in the research measurement portion of the study independently of participation in the intervention. The models will be performed using HLM software. 101 Significance tests for variance components will be based on the likelihood ratio test, tests for fixed effects will be based on the Wald test (i.e., B / SE), and 95% CIs will be computed to reflect the magnitude and precision of the effects.

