Aim 2: Examine whether youth whose caregivers receive prize incentives (CCM) have greater reductions in drug use and criminal re-offending relative to youth receiving treatment as usual (TAU). Aim 2 will be evaluated using a series of two-level MRMs with repeated measurements of drug use and antisocial behavior (level-1) nested within youth (level-2). For urine drug screens (UDSs), the number and spacing of measurements will vary both within and across youth. For the GAIN subscales and SRD, there will be six measurements per youth, scheduled to occur at 0, 3, 6, 9, 12, and 18 months following baseline. The archival criminal charge data, which will be comprised of charge dates within youth, will be evaluated to determine the most appropriate modeling approach. For instance, if charges occur infrequently, the outcome could be the total count of charges during the 18 month period, evaluated using a single-level generalized linear model with a negative binomial outcome distribution. Alternatively, if charges occur more frequently, the outcome could be specified as the count, or any occurrence, during time periods that correspond to the research measurements. The models for Aim 2 will test for differences between CCM and TAU on the drug use and antisocial behavior outcomes at baseline and in the rate (and/or acceleration) of change over time.

Aim 3: Examine whether caregiver attendance and participation explain condition-related changes in youth drug use and criminal offending. Aim 3 will be tested using the product of coefficients

Version: 2017 09 06 Page 20 of 45

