Attrition & missing data. Youth will be retained in the research portion of the study independently of participation in the clinical intervention according to ITT principles (e.g., Nich & Carroll). This strategy, along with the successful participant tracking and retention protocols used in FSRC research, will minimize the amount of missing data. However, some data will inevitably be missing. The methods recommended by Schafer and Graham will be used to evaluate missing data assumptions and determine the best analytic strategy. A three-step approach will be used: First, for a small proportion of missing data and evidence that they are Missing at Random (MAR), the available data will be analyzed using the maximum likelihood-based estimation procedures described above. Second, for a non-trivial amount of missing data and evidence that they are MAR, multiple imputation for repeated measurements will be used to generate complete data. Third, if there is evidence of a non-random missing data mechanism (i.e., NMAR), pattern mixture models will be used to evaluate and control the effect of the missing data pattern in the models.

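### The missing-data method is selected by evidence of MAR or NMAR, which observed outcomes cannot supply, so the only NMAR analysis hangs on an undefined trigger

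*Combined protocol and SAP*

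**What the plan says.** The rule is in the combined protocol and SAP, section 7.0, under the paragraph on attrition and missing data. The plan accepts that retention efforts will not be complete: "However, some data will inevitably be missing". It then says that methods from a cited paper "will be used to evaluate missing data assumptions and determine the best analytic strategy", and sets out three branches:

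1. Likelihood: "for a small proportion of missing data and evidence that they are Missing at Random (MAR), the available data will be analyzed" by the maximum-likelihood procedures already described.
2. Imputation: "for a non-trivial amount of missing data and evidence that they are MAR, multiple imputation for repeated measurements will be used" to complete the data.
3. Pattern mixture: "if there is evidence of a non-random missing data mechanism (i.e., NMAR), pattern mixture models will be used to evaluate and control" for missingness within the outcome models themselves.

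The documents do not define evidence, a small proportion or a non-trivial amount. They do not say who decides, or whether that person has seen results by arm. They do not specify the patterns or identifying restrictions for step 3. No other section commits to an NMAR analysis regardless of what the diagnostics show.

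**The concern.** MAR and NMAR differ only in whether missingness still depends on the unseen values once the observed values are taken into account. A rule that branches on which of the two holds therefore asks the data for something they do not contain.

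Two things follow. Steps 1 and 2 rest on the same MAR assumption, so moving from likelihood to imputation gives no protection against NMAR; only step 3 does, and it waits on a trigger that nobody has defined. And because step 3 is meant to control the effect within the models, invoking it replaces the main analysis instead of adding a robustness check beside it.

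Outcome-related loss is plausible from the protocol itself. Youth may be detained, and follow-up in the facility needs permission (section 3.0.1). Those who withdraw may decline the exit assessment and are then not contacted again (section 3.0.2). Passive non-engagement is foreseen among the stopping rules (section 12.0). Detention and disengagement are plausibly related to drug use and offending, the Aim 2 outcomes. CCM rewards caregiver engagement, so loss could differ between arms. What is at stake is whether a reader of the Aim 2 results will ever see how far they depend on MAR.

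**Working it through.** The plan gives no figure on this point to reproduce: there is no power calculation, dropout rate, outcome rate or effect size. Three checks follow; every rate in them is an assumption unless a source is named.

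**1. Can observed outcomes separate MAR from NMAR?** Take a binary urine-screen result, 30% positive among those observed, 20% missing.

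- MAR model: the missing are also 30% positive. True rate 30%. Observed cells: positive and seen 0.8 × 0.30 = 0.24; negative and seen 0.8 × 0.70 = 0.56; missing 0.20.
- NMAR model: 70% of the missing are positive. True rate 0.8 × 0.30 + 0.2 × 0.70 = 0.38. The chance of being seen is 0.24/0.38 = 0.63 for positives and 0.56/0.62 = 0.90 for negatives. Observed cells: 0.24, 0.56, 0.20.

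The cells are identical, but the true rates are 30% and 38%. At 10% missing the true rates are 30% and 34%; at 30% missing, 30% and 42%; again with identical cells. The same construction works within any group of youth who share the same earlier observed values, so conditioning on history does not rescue the diagnosis.

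**2. What can a departure from MAR do to a binary result?** Assume 90 per arm (the plan has "with random assignment of 180 caregivers/youths to one of the two treatment conditions"; equal allocation is my assumption), observed positive rates of 30% in CCM and 50% in TAU, and 20% missing in each arm. Each arm's full rate is (1 − d) × observed rate + d × rate among the missing. The z-values treat the filled-in data as complete.

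| Positive among missing, CCM / TAU | Full rates | Difference | z |
|---|---|---|---|
| 30% / 50% (MAR) | 30% / 50% | −20 points | −2.80 |
| 70% / 50% | 38% / 50% | −12 points | −1.63 |

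With the second pattern the difference is −16 points (z −2.20) at 10% missing and −8 points (z −1.08) at 30% missing.

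**3. What can it do to a continuous scale?** For a single-time-point difference in means with a departure δ in one arm only: shift = m × δ; SE = √(2 / (90 × (1 − m))); type I error = Φ(−1.96 + shift/SE) + Φ(−1.96 − shift/SE).

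| Missing m | δ (SD) | Shift (SD) | SE | Shift/SE | Type I error |
|---|---|---|---|---|---|
| any | 0 | 0 | – | 0 | 5.0% |
| 8% | 0.5 | 0.040 | 0.155 | 0.26 | 5.8% |
| 15% | 0.3 | 0.045 | 0.162 | 0.28 | 5.9% |
| 20% | 0.5 | 0.100 | 0.167 | 0.60 | 9.2% |
| 25% | 0.5 | 0.125 | 0.172 | 0.73 | 11.2% |

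Equal departures with equal missingness in both arms give zero shift and 5.0%.

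The 8% row is the nearest the documents come to a loss rate. Section 3.0.1 expects 374 youth and caregivers to complete. If the denominator is 180 trial pairs plus 24 pilot pairs, that is 374/408 = 91.7%, or about 8% loss. The denominator is not stated, so this is an assumption too. The 15% to 25% rows have no source in the documents.

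**The case against.** **The plan says evidence, not test, and it collects relevant information.** Therapists record why families leave treatment (Termination Questionnaire, sections 4.0 and 5.0). Probation urine screens and archival arrest, charge and incarceration records may exist when self-reports do not (section 4.0). This stands in part: such information makes NMAR more or less plausible. It does not establish the mechanism, and section 7.0 does not tie the trigger to it.

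**The protocol works to limit loss.** Section 7.0 states "The analyses will use an intention-to-treat approach, with youth/caregivers retained in the research measurement portion of the study independently of participation in the intervention". Section 3.0.1 provides for visits in detention facilities and for a private interview with youth who seem to be disengaging; section 5.0 provides for a further attempt at a missed measure at the next visit. These measures reduce missing data. They do not identify why the rest is missing.

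**Not every outcome is exposed.** Aim 1 attendance is recorded for each scheduled date by court staff, research assistants or therapists, and archival charges come from records. Neither depends on a follow-up visit. This stands. The exposed outcomes are the GAIN scales and the SRD, for which "there will be six measurements per youth, scheduled to occur at 0, 3, 6, 9, 12, and 18 months following baseline", and the urine screens, including those the study itself collects after probation discharge.

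**Stronger readings the documents do not support.** A reader might infer that the plan has no NMAR analysis; it names one, and the defect is that it is conditional and undefined. A reader might infer that the method will be picked for a favourable result; the rule branches on the amount and mechanism of missingness, not on the treatment effect, and the choice between likelihood and imputation matters less because both assume MAR. A reader might also take 6% to 11% as this trial's type I error; those values need a departure in one arm only and an unsourced 15% to 25% missing, at one time point, whereas the planned tests concern change over time in mixed models, including binary outcomes.

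**Conclusion.** The point holds on the logic, with high confidence. The selection rule cannot work as written, because observed outcomes do not show which branch applies. The one analysis that addresses NMAR is therefore not guaranteed, and if invoked it alters the main model after the data are seen. The weakness concerns the visit-dependent Aim 2 outcomes; it does not invalidate the plan.

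The effect on this trial cannot be derived from the documents. The illustrative 5% to about 11% rests on 90 per arm, 8% to 25% missing and a departure of 0 to 0.5 SD in one arm. It should be read as showing that the answer can matter, not as an estimate. This is a change the sponsor should make.

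**What to change.** Replace the three-step branch in section 7.0 with one fixed rule:

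- **Primary.** The likelihood-based mixed-effects regression model under MAR is always the primary analysis. Multiple imputation, if used, is a supporting analysis under the same assumption.
- **Sensitivity, always reported.** An arm-specific pattern-mixture or delta-adjusted analysis, with its tipping point, for the GAIN scales, the SRD and the urine screens, including those collected by the study after probation discharge.
- **Range.** State the deltas in advance. Include zero and equal departures in both arms. Use SD units for continuous scales, the logit or rate scale for urine screens, and the log-rate scale for counts.
- **Dropout reasons.** Use them to interpret the sensitivity result, not to choose the method.
- **Scope.** Leave out Aim 1 attendance and archival charges unless their records prove incomplete.

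The cost is SAP wording and one extra analysis per listed outcome, with no new data collection. The downside is that the sensitivity result may look less favourable than the primary one.

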8.0 DATA MANAGEMENT & PRIVACY/CONFIDENTIALITY

Use of identifiers with private information						
List of identifiers	Looked at by research team	Recorded on an enrollment log, subject list, key list, or stored in a database	Recorded on data collection tools (CRFs, surveys, spreadsheets, etc.)	Recorded on specimen containers	Shared with others (outside research team)	Stored after study completed
Names	\boxtimes	×				\boxtimes

Version: 2017 09 06 Page 21 of 45

a study code that is linked to the individual's identity using a key that is only accessible by the researcher	N/A	\boxtimes	\boxtimes	X		X
Address	\boxtimes	\boxtimes	\boxtimes			\boxtimes
Dates (except year)	\boxtimes	\boxtimes	\boxtimes	\boxtimes		\boxtimes
Phone or Fax numbers	×	×	×			×
E-mail addresses	×	×	×			\boxtimes
Biometric Identifiers, including finger and voice prints Full face photographic images and any comparable images	Specify: Results of urine screens & audio recordings	Specify: Results of urine screens & audio recordings	Specify: Results of urine screens & audio recordings	□ Specify:	□ Specify:	Specify: results of urine screens & audio recordings
All study related measures/assessments	×	×	×	Specify:	Specify:	⊠ Specify:
Any other pre-existing unique identifying number, characteristic, or code: Number associated with juvenile and/or adult arrest records	×	×	×			×

Coding Plan	
Describe the method that will be used to create and assign a unique study code to the data	A unique study identifier will be assigned to each participant corresponding to the order of their enrollment
Describe the method that will be used to create and assign a unique study code to the specimens	The subject's ID will be used for labeling urine specimens. See above for how subject IDs will be assigned.
What is the format of the key?	□Paper ⊠Electronic
Who will have access to the key?	Access to this data is limited to study staff with IRB approval for working on this protocol. Study staff will access identified data for the purpose of data entry and analyses. Study staff requires access to identified data to conduct and monitor the study.
Where will the key be stored and how will it be protected?	Location(s): All results and data will be filed using this identifier, and the codebook (linking the identifier to the participant's name) will be stored in a double password protected file on a university sponsored server that is HIPAA compliant. Data entry and database management will be done in an ongoing manner by project staff using a web-based data entry and project management tool (REDCap) hosted by a university on a password protected server that is password compliant. This interface will provide password protected, secure (128 bit SSL) data entry and project management tools.
	Describe confidentiality measures: All staff will be trained in Human Subjects Protection. There are a series of procedures in place to protect the confidentiality of the participants. Biological specimens (urine samples) and psychiatric screening exams, drug-use information, behavioral and psychometric data will be obtained solely for research purposes. Individuals who elect to participate will be assigned

Version: 2017 09 06 Page 22 of 45

an identification number. PHI will not be transferred to another institution (detailed in the consent form). This transfer will only occur via a secure server that is double password protected. Only IRB approved study staff (who have been granted access) at the institution will have access to the data.

D		1
Data /	Paper data Paper data	Data are designed to be captured using electronic means. However, there may be instances when paper forms are necessary. Paper forms will be handled in one two ways: (1) Immediately scanned into RedCap (see below) and attached as a PDF file to a participant's study record. The remaining hard copies will be destroyed using a shredder. Upon entry into RedCap the paper forms are stored in a double password protected encrypted server. (2) Paper copies will be mailed, signature required, to the Site PI ([name]) at Baylor. Upon arrival at Baylor, the paper forms will be entered into RedCap and then stored in HIPAA compliant, locked filing cabinets, housed within locked offices in the department of Psychology and Neuroscience.
×	Electronic data	A MUSC (see coordinating center information below) laptop with encryption will be used to administer some of the research questionnaires. Data will be collected via the Research Electronic Data Capture (REDCap; a data collection tool) and managed using SPSS. Data quality will be ensured by real-time data validation in REDCap and standard data cleaning procedures in SPSS. This study will use REDCap hosted at the Medical University of South Carolina (MUSC; a collaborating site; and PI of the Sponsor Protocol) and is a secure (128 bit SSL), webbased application designed exclusively to support data capture for research studies. Other research questionnaires will be hand entered into REDcap by research staff using desktop computers
		plugged into the Baylor server. Voice recordings and participant tracking logs will be stored on Box hosted by Baylor. Non-identifying information obtained via voice recording and tracking logs will be uploaded to Box at MUSC, a collaborating site and PI of the Sponsor Protocol. Box is a MUSC approved online file sharing system that is a secure and HIPAA compliant way to organize and store data. MUSC has signed a "business associate agreement (BAA) with Box that provides additional security safeguards for sharing protected data.
\boxtimes	Specimens	Biological specimens (urine samples) will be obtained solely for research purposes. Urine samples will be tested

Version: 2017 09 06 Page 23 of 45

		for drugs of abuse immediately and then the collection cups and testing strips will be disposed of immediately.
×	Long-term storage (following completion of the study and inactivation of IRB approval)	Data will be stored in RedCap, the Box, and Baylor protected servers.

Sha	Sharing of Research Data/Specimens to Entities Outside Baylor University									
Entity		Identifiabl e materials		e materials		Limi Data (i.e. m includ elemen dates, state,	Set ay e nts of city,	Non- identi mater		Describe how the materials will be transferred from one location to another.
		Viewed	Transferred	Viewed	Transferred	Viewed	Transferred			
⊠	Coordinating Center: Medical University of South Carolina			X	X	☒	☒	Describe: Data will be collected via and entered into the Research Electronic Data Capture (REDCap) hosted at the Medical University of South Carolina (MUSC) and is a secure (128 bit SSL), web-based application designed exclusively to support data capture for research studies. Additionally, data will be stored on the Box hosted at MUSC. The box is a MUSC approved online file sharing system that is a secure and HIPPA compliant way to organize and store data. MUSC has signed a "business associate agreement (BAA) with Box that provides additional security safeguards for sharing protected data.		
×	Other sites, investigators or collaborators participating in this study. Specify: Alliant International University, Wayne State University			⊠	☒	☒	⊠	Describe: Collaborators participating in this study will have access to the same REDCap and Box described above. Collaborating institutions are deferring to MUSC for IRB review.		

Study Intervention(s)						
Study Intervention(s)			Who will	administer the in	tervention?	
	Routine or Research Only	# encounters per subject	Research Team	Study Site Employees	Commerci al Source	Other
Caregiver Contingency	Research	16		X		Providers at

Version: 2017 09 06 V3 Page 24 of 45

Management			Center for
			Health Care
			Services,
			Family
			Services
			Association,
			and Elite
			Counseling
			where
			therapist are
			also study
			participants

Laboratory/Specimen colle	ection						
Laboratory procedures Who is performing the lab procedure							
		# Procedures (per	Research	Study Site Employees/Services			
		subject)	Team	Obtain specimen	Perform the analysis		
Urine Specimens		Up to 6	×	Research assistant affiliated with Baylor University	Research assistant affiliated with Baylor University		

ALL Other Research Activities						
Activities, Procedures,		Who is perf	Who is performing the activity / service?			
Services, Surveys, Chart Reviews, Tests, etc.	# Research Activities (per	Research	Study Site Employees/S	-		
	subject)	subject) Team	Collect	Perform the analysis		
Eligibility Screener	1	×	Research assistant affiliated with Baylor University	Baylor University; Medical University of South Carolina Alliant International University		

Version: 2017 09 06 Page 25 of 45

		 		T T
				Wayne State University
Demographics and Service Utilization Survey	1			Baylor University ; Medical
		\boxtimes	Research assistant affiliated	University of South Carolina
			with Baylor University	Alliant International University
				Wayne State University
Demographics -Youth	1			Baylor University;
		×	Research assistant affiliated	Medical University of South Carolina
			with Baylor University	Alliant International University
				Wayne State University
Demographics – Therapist	1			Baylor University;
		×	Research assistant affiliated	Medical University of South Carolina
			with Baylor University	Alliant International University
				Wayne State University
Demographics – Juvenile Drug Court	1	×	Research assistant affiliated	Baylor University ; Medical
			with Baylor University	University of South Carolina

Version: 2017 09 06 Page 26 of 45

	T		1		1	-
				Alliant International University Wayne State University		
Child Behavior Checklist	6			Baylor University;		
		×	Research assistant affiliated with Baylor University	Medical University of South Carolina Alliant International University		
				Wayne State University		
Brief Problem Checklist - Caregiver	4			Baylor University;		
			Research assistant	Medical University of South Carolina		
			affiliated with Baylor University	Alliant International University		
				Wayne State University		
Brief Problem Checklist - Youth	10			Baylor University;		
		×	Research assistant affiliated	Medical University of South Carolina		
			with Baylor University	Alliant International University		
				Wayne State University		
Addiction Severity Index Self-Report	2	×	Research assistant affiliated	Baylor University;		

Version: 2017 09 06 Page 27 of 45

			with Baylor University	Medical University of South Carolina Alliant International University Wayne State University
Beck Depression Inventory-II	2	×	Research assistant affiliated with Baylor University	Baylor University; Medical University of South Carolina Alliant International University Wayne State University
Working Alliance Inventory – Caregiver	5	X	Research assistant affiliated with Baylor University	Baylor University; Medical University of South Carolina Alliant International University Wayne State University
Working Alliance Inventory – Youth	5	X	Research assistant affiliated with Baylor University	Baylor University; Medical University of South Carolina Alliant International University Wayne State University

Version: 2017 09 06 Page 28 of 45

		 		
Working Alliance Inventory – Therapist Report on Caregiver	5	⊠	Research assistant affiliated with Baylor University	Baylor University; Medical University of South Carolina Alliant International University Wayne State University
Working Alliance Inventory – Therapist Report on Youth	5	×	Research assistant affiliated with Baylor University	Baylor University; Medical University of South Carolina Alliant International University Wayne State University
Caregiver Contingency Management Session Tracking Sheet	20	X	Research assistant affiliated with Baylor University	Baylor University; Medical University of South Carolina Alliant International University Wayne State University
Caregiver Treatment as Usual Session Tracking Sheet	20	×	Research assistant affiliated with Baylor University	Baylor University; Medical University of South Carolina Alliant International

Version: 2017 09 06 Page 29 of 45

				University	
				Wayne State University	
Homework Rating Scale – Caregiver	20		Research assistant affiliated with Baylor University	Baylor University; Medical University of South Carolina Alliant International University Wayne State University	
Homework Rating Scale – Therapist	20	X	Research assistant affiliated with Baylor University	Baylor University; Medical University of South Carolina Alliant International University Wayne State University	
Client Satisfaction Questionnaire – JDC Version	1		Research assistant affiliated with Baylor University	Baylor University; Medical University of South Carolina Alliant International University Wayne State University	
Client Satisfaction Questionnaire – Clinic Version	1	⊠	Research assistant affiliated with Baylor University	Baylor University; Medical University of South	

Version: 2017 09 06 Page 30 of 45

Termination Questions I Research assistant affiliated with Baylor University Qualitative Interview— Caregiver Qualitative Interview— Therapist Qualitative Interview— I Research assistant affiliated with Baylor University Research assistant affiliated with Baylor University Wayne State University; Medical University Wayne State University; Medical University of South Carolina affiliated with Baylor University Research assistant affiliated with Baylor University Wayne State University			 		Compliance
Termination Questions					Carolina
Termination Questions I Baylor University Medical University Wayne State University of South Alliant International University Wayne State University Wayne Stat					
Termination Questions I Baylor University; Medical University South Carolina affiliated with Baylor University Wayne State University Wa					1 1
Termination Questions I Baylor University in Medical University in Medical University of South Carolina affiliated with Baylor University in Medical Univ					
Qualitative Interview— Caregiver Qualitative Interview— Caregiver Qualitative Interview— Caregiver Research assistant affiliated with Baylor University Wayne State University; Medical University Wayne State University; Medical University; Medical University; Medical University of South Carolina affiliated with Baylor University Wayne State University; Medical University Wayne State University Wayne State University; Medical University Wayne State University					
Qualitative Interview— Caregiver Qualitative Interview— Caregiver Qualitative Interview— Caregiver Research assistant affiliated with Baylor University Wayne State University; Medical University Wayne State University; Medical University; Medical University; Medical University of South Carolina affiliated with Baylor University Wayne State University; Medical University Wayne State University Wayne State University; Medical University Wayne State University	Tarmination Quarticus				-
Qualitative Interview — Therapist Qualitative Interview — Therapist Qualitative Interview — Research assistant affiliated with Baylor University Qualitative Interview — Research assistant affiliated with Baylor University Qualitative Interview — Research assistant affiliated with Baylor University Qualitative Interview — Research assistant affiliated with Baylor University Qualitative Interview — Research assistant affiliated with Baylor University Qualitative Interview — Research assistant affiliated with Baylor University Qualitative Interview — Research assistant affiliated with Baylor University Qualitative Interview — Research Baylor Qualitative Interview — Research Baylor	1 emmation Questions	1			
Qualitative Interview — Caregiver Qualitative Interview — Therapist Qualitative Interview — Therapist Qualitative Interview — Therapist Qualitative Interview — Research assistant affiliated with Baylor University Qualitative Interview — Therapist Qualitative Interview — Therapist Alliant Interview — Therapist Alliant Interview — Therapist Alliant Interview — Therapist Alliant Interview — Ther					Medical
Qualitative Interview — Caregiver Qualitative Interview — Therapist Qualitative Interview — Therapist Alliant International University Qualitative Interview — Therapist Alliant Interview —					University of
Qualitative Interview — Caregiver Qualitative Interview — Caregiver I Research assistant affiliated with Baylor University Qualitative Interview — I Research assistant affiliated with Baylor University Qualitative Interview — I Research assistant affiliated with Baylor University Qualitative Interview — I Research assistant affiliated with Baylor University Qualitative Interview — Research assistant affiliated with Baylor University; Qualitative Interview — Research assistant affiliated with Baylor University of South Carolina Alliant International University Wayne State University Qualitative Interview — Research Baylor					
Qualitative Interview — Caregiver Qualitative Interview — Caregiver Research assistant affiliated with Baylor University Qualitative Interview — Therapist Qualitative Interview — Therapist Qualitative Interview — Therapist Qualitative Interview — Therapist Qualitative Interview — Research assistant affiliated with Baylor University Wayne State University Medical University Wayne State University of South Carolina Alliant International University Wayne State University			\boxtimes		Alliant
Qualitative Interview — Caregiver Academic and the properties of the properties o					International
Qualitative Interview – Caregiver Research assistant affiliated with Baylor University Qualitative Interview – Therapist Qualitative Interview – Therapist Research assistant affiliated with Baylor University Research assistant affiliated University Research assistant affiliated University; Research assistant affiliated University of South Carolina affiliated University Wayne State University Qualitative Interview – Research Baylor Qualitative Interview – Research Baylor					University
Qualitative Interview – Caregiver A					
Caregiver Research assistant affiliated with Baylor University Qualitative Interview − Therapist Research assistant affiliated with Baylor University Research assistant affiliated university Research assistant affiliated with Baylor University of South Carolina Research assistant affiliated with Baylor University Alliant International University of South Carolina Alliant International University Wayne State University Wayne State University Qualitative Interview − Qualitative Interview − Research Baylor					University
Research assistant affiliated with Baylor University Qualitative Interview − Therapist I Research assistant affiliated with Baylor University Research assistant affiliated with Baylor University; Medical University Wayne State University; Medical University Wayne State University of South Carolina affiliated with Baylor University of South Carolina affiliated with Baylor University of South Carolina affiliated with Baylor University Qualitative Interview − Qualitative Interview − I Research Baylor Wayne State University Wayne State University		1			
Research assistant affiliated with Baylor University Qualitative Interview – Therapist Research assistant affiliated with Baylor University Qualitative Interview – Therapist Research assistant affiliated with Baylor University of South Carolina affiliated with Baylor University Qualitative Interview – Research assistant affiliated with Baylor University Qualitative Interview – Research Baylor	Caregiver				
Research assistant affiliated with Baylor University Qualitative Interview − Therapist Qualitative Interview −					
Qualitative Interview − I Therapist Baylor University Wayne State University Wayne State University; Medical University of South Carolina affiliated affiliated with Baylor University With Baylor University Wayne State University of South Carolina affiliated university With Baylor University Wayne State University Qualitative Interview − I Research Baylor					South
University University University Wayne State University Wayne State University: Research assistant affiliated with Baylor University Alliant International University Wayne State University of South Carolina Alliant International University Wayne State University Wayne State University Qualitative Interview − Qualitative Interview − Research Baylor			\boxtimes		Carolina
University Wayne State University Qualitative Interview − Therapist I Research assistant affiliated with Baylor University Alliant International University Wayne State University Wedical University of South Carolina Alliant International University Wayne State University Wayne State University Wayne State University					
Qualitative Interview – Therapist I Research assistant affiliated with Baylor University Wayne State University Qualitative Interview – Qualitative Interview – I Research assistant affiliated with Baylor University Research South Carolina Alliant International University Wayne State University Qualitative Interview – I Research Baylor				University	
